1.0 INTRODUCTION

Patients with chronic intractable pain of the trunk and/or limbs are typically treated on a continuum with less invasive therapies prescribed first. Established, non-surgical treatment options include, but are not limited to, oral medications, physical therapy, TENS, acupuncture, nerve blocks, radiofrequency ablation and other options based on clinical judgment. The surgical treatment options for these patients include surgery of the spine, sympathectomy, intrathecal drug pumps, and spinal cord stimulation (SCS) systemsⁱ.

An advantage of a SCS system is that it is a reversible and nondestructive treatment option. The main principle of SCS therapy is pain suppression via the delivery of electrical signals to the spinal cord and related nerves through electrodes in the epidural space. An implantable pulse generator (IPG) is implanted under the skin, typically in the abdomen or buttock area, to generate mild electrical signals. The electrical signals typically produce paresthesia overlapping the area of pain for the patient. The IPG is programmed to deliver the electrical signals in a therapeutic manner and is then activated by the patient as needed to assist in management of their pain. SCS therapy treatment is deemed successful if there is a 50% reduction in pain as measured by a numeric rating scale or visual analog scale. The most common use of SCS therapy is for failed back surgery syndrome (FBSS) that affects up to 40% of patients who undergo spinal surgeries^{ii iii iv v}.

A candidate for SCS therapy is first tested by undergoing a trial procedure in which a temporary lead is implanted in the epidural space and then externalized and connected to external pulse generator (EPG). A temporary trial typically last 5 to 10 days and will allow the patient and doctor to determine the effectiveness of the therapy before undergoing a permanent implant.

SCS therapy has been in use since the early 1970s and has been implanted in over 600,000 patients to treat chronic pain. Over the past 30 years, SCS system technology has advanced from single channel IPGs with single contact leads to multi- channel IPGs with over 32 channels, rechargeable batteries, and lead designs improved for reliability and stability. Though the principles of operation of the SCS system have essentially remained the same, these advances have increased safety, efficacy and longevity of the therapy.

The Algovita® SCS System is similar in design and performance to newer SCS systems from other medical device companies. The FDA approved Algovita® system has many advanced features including the ability to better control the shape of the electrical pulse. One such feature is a longer pulse width range than the other systems on the market. Pulse width determines how long an electrical pulse is activated. A longer pulse width is not associated with any safety concerns as determined by the FDA. The intent and justification for this study is to understand if a longer pulse width provides better outcomes to patients.

Although the effects of pulse width are mentioned in many SCS investigations, it has been the primary focus of very few studies. Several decades ago, research was conducted into the technical aspects of SCS, including PW. In a study of SCS, Jobling showed that different patients required widely varying amplitudes of stimulation and concluded that 200 μ sec was the optimum pulse duration, because it was the most energy- efficient^{vi}. In 1980, Davis and Gray concurred that 200 μ sec was the preferred PW to deliver adequate amplitude while conserving energy^{vii}. Some published reports suggested that there was therapeutic value to having higher parameter ranges than were available on previous primary cell IPGs. In addition, longer PWs have been anecdotally described as achieving better pain-paresthesia overlap and comfort for the patient, thus potentially more effective at relieving pain^{viii}.

The introduction and widespread adoption of rechargeable IPGs for SCS has diminished the importance of energy efficient programming to prolong time between revision surgeries and resulted in longer pulse width settings in these systems. Gould and Bradley reported in a retrospective analysis of patient-preferred programs that over 50% of the programs used PWs in excess of 450 μ s^{ix}. Yearwood et al. showed that 10/19 patients had greater coverage, and 8/19 patients displayed “caudal shift” of paresthesia coverage with increased PW^x. A mathematical model of electrical field and neural activation in SCS has shown good agreement with clinical data that a longer PW is associated with increased paresthesia coverage and a shift of the paresthesia coverage caudally^{xi}.

Investigation into the clinical and technical effects of PWs may be important in the continued effort to more fully understand the mechanisms of SCS. In other neurostimulation applications, varied PW has been shown to provide large and small fiber neural selectivity, where shorter PWs maximized the difference between large and small fiber thresholds^{xii}. With advances in SCS technology, particularly rechargeable IPGs, patients are now being offered a wider range of parameters to treat their pain. In particular, PW programming ranges of the Algovita® system can be programmed up to 1500 μ sec).

2.0 OBJECTIVES

2.1 Primary Objective

To evaluate the effect of conventional pulse widths <500 μ sec and pulse widths >1000 μ sec on clinical outcomes during temporary trial as measured by patient defined pain maps.

2.2 Secondary Objectives

Secondary measures of therapy effectiveness will include:

1. To evaluate the effect of conventional pulse widths <500 μ sec and pulse widths >1000 μ sec on clinical outcomes during temporary trial as measured by the percent reduction in targeted pain compared to baseline using the NRS at the end of the trial period.
2. At end of each arm, subjects will be asked to complete a diagram that shows distribution of paresthesia.
3. At the end of the trial period, subjects will be asked to select their favorite program.
4. At the end of the trial period, subjects will be asked to rate the quality of the pain relief achieved during the trial (from either arm) using the following scale; *Excellent, Very Good, Good, Fair or Poor*
5. At the end of the trial period, subjects will be asked to rate their overall satisfaction with the pain relief achieved during the trial (from either arm) using the following scale; *Very Satisfied, Satisfied, Neither Satisfied nor Unsatisfied, Unsatisfied or Very Unsatisfied*
6. Number of patients who achieved $\geq 50\%$ pain relief during the trial (from either arm)
7. Rate of device-related and/or procedure-related AEs from SCS implant through study completion or study exit.

3.0 DEVICE

3.1 ALGOVITA® SPINAL CORD STIMULATION SYSTEM

This Clinical Study will include commercially released system components from the Algovita® SCS System manufactured by Nuvectra® Corporation (Plano, Texas). The materials, dimensions, method of construction, indications for use, and principles of operation of the Algovita® SCS system components are the same or functionally similar to the FDA-approved and CE marked products distributed by Medtronic, Abbott (St. Jude), and Boston Scientific.

The Algovita® SCS system is indicated as an aid in the management of chronic intractable pain of the trunk and/or limbs, including unilateral or bilateral pain associated with failed back surgery syndrome, intractable low back pain and leg pain.

The devices used for this study will be sourced through normal commercial channels from Nuvectra® and will not be supplied by the Sponsor.

3.2 REGULATORY CLASSIFICATION

The Algovita® SCS System received CE Mark in Europe on 14 June 2014 and FDA (PMA) approval in the US on 20 November 2015.

The sponsor has determined that this qualifies as a post-market study. The SCS system is being used per labeling indications and data collection have been aligned with typical data collection for SCS systems.

4.0 STUDY DESIGN

The proposed study is a prospective, single-center, two arm, randomized, crossover design to be conducted at The Ohio Pain Clinic. The study will enroll up to 100 subjects in order to assure at least 50 subjects in the study. Subjects selected to participate in the trial have back and/or leg pain, have been identified as a candidate for SCS and have agreed to undergo a temporary SCS trial using the Algovita® system with percutaneous leads. Each subject will be followed during the trial period of approximately 7 days.

The study will end when the last subject has completed the trial period or is exited. The expected enrollment period for this study is approximately three months. After exit from the clinical study, subjects will continue to be followed by their physician per usual care. All device and procedure-related AEs will be collected and reported per the study protocol.

4.1 OVERVIEW OF DATA COLLECTION AT STUDY VISITS

Assessments and Data Collection	Enrollment	Baseline	After Implant	Follow-up Visits	Study Exit
• Eligibility confirmation	✓				
• Medical history		✓			
• Physical exam	✓				
• Informed consent	✓				
• Record demographics		✓			
• Brief Pain Inventory		✓			
• Record pain map		✓			
• Implant and system information			✓		
• Record paresthesia and pain map for current arm			✓	✓	✓
• Record pain rating for current arm	✓	✓	✓	✓	✓
• Document any AEs	✓	✓	✓	✓	✓
• Record subject program preference					✓
• Record subject satisfaction and pain relief from each program					✓
• Document study exit reason & any AEs					✓

Figure 4.1 Study Flowchart

5.0 ENDPOINTS

The endpoints of the study are focused on collecting data to determine clinical outcomes of Pulse Widths $>1000\mu\text{sec}$ compared to Pulse Widths $<500\mu\text{sec}$ during an SCS trial. Safety data will also be collected at all visits. Data will be collected using:

- Patient generated Pain Maps
- The NRS to assess pain levels
- Questionnaires to assess pain coverage, program preference, overall satisfaction of the trial and AEs

5.1 PRIMARY EFFECTIVENESS ENDPOINT

The primary effectiveness endpoint is defined as the percent reduction from baseline in targeted patient generated pain map coverage between the two arms.

5.2 SECONDARY ENDPOINTS

Endpoints for secondary measures of therapy effectiveness:

- To evaluate the effect of conventional pulse widths and pulse widths $>1000\mu\text{sec}$ clinical outcomes during temporary trial as measured by the percent reduction in targeted pain compared to baseline using the NRS at the end of the trial period.
- Comparison of paresthesia overlap of pain between each arm as evaluated by the reviewer to determine which arm had superior pain overlap (coverage)
- Patient *preference* for pulse widths $>1000\mu\text{sec}$ or $<500\mu\text{S}$
- Patient *satisfaction* for pulse widths $>1000\mu\text{sec}$ or $<500\mu\text{S}$
- Number of patients who achieved $\geq 50\%$ pain relief during the trial (from either arm)
- Rate of device-related and/or procedure-related AEs from Trial Lead implant through study completion.

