- Compare the change from baseline of pain scores between the two study arms. Pain scores are obtained using the Numeric Rating Score (NRS) administered at baseline and after completion of each arm of the study.
- Paresthesia distribution: At end of each arm, subjects will be asked to complete a diagram that shows distribution of paresthesia.
- At the end of the trial period, subjects will be asked to select their favorite program.
- At the end of the trial period, subjects will be asked to rate the quality of the pain relief achieved during the trial (from either arm) using the following scale; *Excellent, Very Good, Good, Fair or Poor*.
- At the end of the trial period, subjects will be asked to rate their overall satisfaction with the pain relief achieved during the trial (from either arm) using the following scale: *Very Satisfied, Satisfied, Neither Satisfied nor Unsatisfied, Unsatisfied, or Very Unsatisfied*.

Secondary Safety Objectives Secondary measures of therapy safety will include:

- Rate of device-related and/or procedure-related AEs from the Trial procedure through study completion.

Study Procedures After the subject has consented to the study, he or she will be enrolled in the clinical study and undergo a baseline evaluation. The patient will then be randomly assigned to arm one (pulse width <500 μ sec) or arm two (pulse width >1000 μ sec) and undergo an Algovita® trial procedures. Following the trial procedure, the subject's EPG will be set to the appropriate pulse width, based on the arm assigned, and then programmed to achieve optimal pain relief. For the next three days, the subject will evaluate pain relief generated by the 1st assigned program (arms).

After 3 days, the patient will visit the Ohio Pain Clinic for data collection and then reprogramming of the EPG for the next arm. For the next three days, the subject will evaluate the SCS therapy generated by the 2nd assigned program and then return to the clinic for data collection, removal of the leads and exit from the study. After the subject is exited from the study, he or she will be followed by the Ohio Pain Clinic per usual care. The data collection requirements are listed below.

Enrollment:

- Informed consent signed
- Confirmation of study eligibility

Baseline evaluation:

- Record pain ratings and pain map
- Relevant medical history
- Physical examination
- Brief Pain Inventory
- Demographics

After the lead implantation:

- Implant procedure

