6.0 MINIMIZATION OF BIAS

Potential sources of bias in this study may result from selection of subjects, treatment of subjects, and evaluation of study data. The following methods have been incorporated into the study to minimize potential bias.

- Subjects will be screened to confirm eligibility for enrollment with defined inclusion/exclusion criteria prior to enrollment
- Subject demographics will be collected at baseline on possible differences that may affect the primary objective
- All study clinicians, participating site personnel, and the Sponsor's personnel will be trained on their respective aspects of the study using standardized training materials
- All study clinicians will be trained on and required to follow the CIP

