8.0 STUDY POPULATION

Subjects that are candidates for SCS, agreed to undergo an SCS temporary trial and that meet study eligibility criteria will be asked to participate in the study and will be required to sign informed consent prior to any study-related procedures or data collection occurring. It is expected that up to 15 subjects may be enrolled to screen for eligibility, and up to 10 subjects will undergo an SCS trial with the Algovita® Trial System. Subjects may either be male or female and must meet all eligibility criteria noted below which are typical eligibility criteria for SCS system post-market studies.

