9.0 Methods and Procedure

9.1 DATA COLLECTION REQUIREMENTS

Subject data will be collected and documented on case report forms (CRFs). Drafts of the CRFs for this study are located in Appendix 17.

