9.1.6 STUDY EXIT

A Study Exit CRF must be completed for any subject who signed an informed consent form, as they are considered enrolled in the study. Data to be collected at this visit includes:

- Record paresthesia and pain map for current arm
- Record pain rating for current arm
- Record program preference

- Record satisfaction and pain relief from each program
- Study exit date and reason for study exit

Additional data that will be collected as they occur include:

- Device or procedure related AEs
- Technical Observations/Device Deficiencies
- Surgical Interventions

The following scenarios may lead to study exit and will require completion of a Study Exit CRF.

- Inclusion/exclusion criteria not met
- Subject ineligibility for implant, in the opinion of the study physician
- SCS lead removal without re-implantation
- Implant attempted, however no SCS was implanted
- Voluntary withdrawal by subject
- Investigator chooses to withdraw a subject
- Failure to maintain adequate study compliance
- Subject Death

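### The supplied protocol does not mask the reviewer who judges which arm had better paresthesia overlap, or the patients; coded maps, a fixed overlap rule and neutral program labels are a cheap improvement

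*Combined protocol and SAP*

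**What the plan says.** **The endpoint.** Section 5.2 lists as a secondary endpoint: "Comparison of paresthesia overlap of pain between each arm as evaluated by the reviewer to determine which arm had superior pain overlap (coverage". The reviewer is not identified, and no scoring rule or reference map is given.

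**The bias controls.** Section 6.0 opens: "Potential sources of bias in this study may result from selection of subjects, treatment of subjects, and evaluation of study data". It then lists four measures: eligibility screening, collection of demographics, standardized training, and adherence to the investigational plan.

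**The expected direction.** The Introduction (section 1.0) says that "longer PWs have been anecdotally described as achieving better pain-paresthesia overlap and comfort for the patient". It also cites a clinical study in which 10 of 19 patients had greater coverage with increased pulse width, and a model agreeing with clinical data that "a longer PW is associated with increased paresthesia coverage and a shift of the paresthesia coverage caudally". The stated intent is still to find out whether longer is better.

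**The maps.** A pain map is drawn at baseline (section 9.1.3). Sections 9.1.5 and 9.1.6 each add: "Record paresthesia and pain map for current arm". The table in section 4.1 schedules the same item after implant as well. The secondary objectives in the synopsis place the paresthesia diagram at the end of each arm.

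**The patient-reported outcomes.** The primary endpoint (section 5.1) comes from a pain map that the patient generates. The NRS and satisfaction are also patient-reported, and for preference the plan says: "At the end of the trial period, subjects will be asked to select their favorite program".

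**Documents not supplied.** Section 9.1 says: "Drafts of the CRFs for this study are located in Appendix 17". Neither those forms nor the training materials of section 6.0 are available here, and the flowcharts are not shown.

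**The concern.** A comparative call by a reader is most exposed to bias when the two maps are close, the reader knows which arm is which, and the reader has a reason to expect one answer. The Introduction supplies that reason, and nothing in the supplied text removes the knowledge. The lack of a rule adds discretion: with a pain map at baseline and another in each arm, overlap can be measured against different references, and either arm might look better depending on the choice.

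Two things are at stake, and they differ in how far they can be repaired. The reviewer's reading concerns one secondary endpoint, and stored maps could be re-read masked later, although that is weaker than a masked reading fixed beforehand. What patients expect when they draw the map, rate pain or choose a program enters the data at the source. It reaches the primary endpoint, and masking the reviewer does not correct it.

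**Working it through.** **Step 1: match the named bias source with the listed controls (section 6.0).** The source in question is evaluation of study data.

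| Listed control | Conceals the arm from the reviewer? | Conceals it from the patient? |
|---|---|---|
| Eligibility screening | No | No |
| Baseline demographics | No | No |
| Standardized training | Not as described; content not supplied | Not as described |
| Following the investigational plan | No; the plan contains no masking rule | No |

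**Step 2: look elsewhere.** The synopsis procedures set the stimulator to the assigned pulse width. Section 9.1.4 lets a manufacturer representative help with programming. Sections 9.1.5 and 9.1.6 describe the data collected at each visit. Sections 11.1 and 11.2 define populations and name general tests under a safety heading. None mentions masking, coded maps, neutral labels or an overlap rule. None calls the study open-label either.

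**Step 3: what the endpoint leaves to choose.** The reference pain map could be the baseline map or a map from either arm. For the first arm, the paresthesia map could be the post-implant one (table in section 4.1) or the end-of-arm one (synopsis). Section 5.2 settles neither.

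**Step 4: illustration of reviewer bias.** The plan gives no figure to reproduce: no test is assigned to this endpoint, and section 8.3 gives only a cap of 100 patients. The test, the share of close calls and the lean below are all assumptions. The sizes 50 and 100 come from section 4.0.

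Assume that the arms are truly equal, that every patient yields a call for one arm, and that an exact two-sided 5% sign test is used. Let f be the share of near-ties and g the share of those given to the longer pulse width. The remaining calls split evenly, so

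P(longer chosen) = (1 − f) × 0.5 + f × g.

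The test rejects at a 33–17 split or wider for N = 50 (p = 0.033; 32–18 gives 0.065), and at 61–39 or wider for N = 100 (p = 0.035; 60–40 gives 0.057). Rejections in either direction are counted.

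| f | g | P(longer chosen) | False positive, N = 50 | False positive, N = 100 |
|---|---|---|---|---|
| – | no lean | 0.50 | 3.3% | 3.5% |
| 0.2 | 0.6 | 0.8 × 0.5 + 0.2 × 0.6 = 0.52 | 4.0% | 5.0% |
| 0.2 | 0.7 | 0.40 + 0.14 = 0.54 | 6.2% | 9.7% |
| 0.2 | 0.8 | 0.40 + 0.16 = 0.56 | 10.0% | 18.3% |
| 0.4 | 0.6 | 0.30 + 0.24 = 0.54 | 6.2% | 9.7% |
| 0.4 | 0.7 | 0.30 + 0.28 = 0.58 | 15.8% | 30.8% |
| 0.4 | 0.8 | 0.30 + 0.32 = 0.62 | 33.5% | 62.4% |

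The unrounded corner value at N = 50 is 0.3348, hence 33% in whole numbers. Even in that corner the expected split at N = 50 is 31–19 (50 × 0.62 = 31), which is not itself significant (p = 0.12).

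The table shows only that the result follows the assumed lean and that a larger sample makes a fixed lean more harmful. The effect of patient expectation cannot be illustrated this way, because the documents give nothing on its size.

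**The case against.** **Silence is not unmasked reading.** A reader might infer that section 5.2 prescribes a reading with the arm in view, or that the study is open-label. The documents say neither, and they do not say that patients are told their pulse width. The draft CRFs, training materials and flowcharts, where a reading procedure could sit, were not available. This stands, so the point is worded conditionally: a safeguard is missing from the supplied text, but no bias has been shown.

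**The figures are not evidence about this trial.** A reader might take 33% or 62% as the error rate of the endpoint. It is not. Both come from the extreme corner of assumed inputs, the low end is almost no harm, and if the endpoint is only described, a false-positive rate has no meaning. This also stands; the figures carry no weight for severity.

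**A trial of 10.** Section 8.0 says "up to 10 subjects will undergo an SCS trial", which might suggest a third row at N = 10. The synopsis gives 10 as a per-site count with up to 100 overall, so that row is not warranted.

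**Limited reach.** This is one of several secondary endpoints in a post-market study of a marketed system, maps can be re-read, and sensation or a caudal shift may reveal the arm whatever is done. That argues against treating the gap as critical. It does not remove the point: the protocol itself names this bias source, a fixed rule narrows discretion even where masking fails, and patient expectation reaches the primary endpoint and cannot be re-read away.

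**Conclusion.** The point holds as a cheap improvement that should be made before enrolment. No supplied section masks the reviewer or the patients, and section 6.0 names evaluation of data as a bias source without a control that conceals the arm. If the reviewer sees the arm, close calls on the overlap endpoint could lean towards the longer pulse width. If patients know the setting, the primary pain map, NRS, preference and satisfaction could be affected too.

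The size of either effect is unknown. The conclusion rests on the missing safeguard and on the direction of expectation in the Introduction, which is partly anecdote and partly a clinical study and a model. Confidence is moderate, because the unsupplied forms or training materials may already contain the procedure.

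**What to change.** In sections 5.2 and 6.0:

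1. **Coded reading by the existing reviewer.** The reviewer reads the end-of-arm paresthesia map from each arm, not the post-implant map, against one reference pain map fixed in advance (for example baseline). Arm, pulse width, visit and date are removed and the two maps are shown in random order. Superior means the larger share of the reference map covered by paresthesia. A call of no difference is allowed, and the call is locked before decoding.
2. **Neutral labels.** The programs are called A and B to the patient until the exit questionnaires are complete. This fits the existing question about a favorite program.
3. **If it is already done.** Where the Appendix 17 forms or the training materials already provide any of this, say so in 5.2 and 6.0.

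**Cost.** A coding log and relabelled forms, with no added visits, patients or devices. No-difference calls leave fewer informative pairs: if the assumed 20% to 40% of near-ties were all called so, 50 patients would leave 40 to 30 pairs (50 × 0.8 and 50 × 0.6) and 100 would leave 80 to 60. Masking stays incomplete, because sensation or a caudal shift may reveal the arm and the person programming still knows the setting.

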8.3 Sample Size

The study sample size is limited to 100 subjects.

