9.1.5 FOLLOW-UP VISITS

Follow-up visits will occur at day 4 and 7 (+/-2) post-implantation. Data collected at these visits will be recorded on case forms (CRFs) and will include:

- Record paresthesia and pain map for current arm
- Record pain rating for current arm
- Document AEs
- Program subject with next arm parameters and document

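### The paresthesia-overlap endpoint records only which arm was judged superior, with no amount of overlap and no tie outcome, so it cannot estimate how much coverage is gained

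*Combined protocol and SAP*

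**What the plan says.** The endpoint in Section 5.2 is "Comparison of paresthesia overlap of pain between each arm as evaluated by the reviewer to determine which arm had superior pain overlap (coverage"). Neither that section nor any other states an amount of overlap, a scoring rule, an outcome for equal arms, or a test for this endpoint. The only named tests are in Section 11.2, under Safety Analysis.

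The matching objective in Section 2.2 is wider: "At end of each arm, subjects will be asked to complete a diagram that shows distribution of paresthesia". A baseline pain map is taken (Section 9.1.3), and the follow-up and exit visits both list "Record paresthesia and pain map for current arm" (Sections 9.1.5 and 9.1.6). The primary endpoint already puts map coverage on a percentage scale: "percent reduction from baseline in targeted patient generated pain map coverage between the two arms" (Section 5.1).

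The design in Section 4.0 is a "two arm, randomized, crossover design", so each subject provides a comparison of the two arms. Section 4.0 gives 50 as the intended minimum number of subjects. Section 8.3 says "The study sample size is limited to 100 subjects", with no significance level, power, effect size or SD behind that number.

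**The concern.** The rationale in Section 1.0 concerns quantity. It cites a clinical study and a mathematical model that associate longer pulse width with greater paresthesia coverage. An endpoint that names only the better arm treats a barely visible difference and a complete one alike. It yields a share of wins and no estimate of added coverage, although the drawings needed for such an estimate are planned.

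Two further matters follow from the wording. The plan does not say how a subject with equal overlap in both arms is recorded. And if each subject contributes one binary call, the natural analysis is a sign-type test, which can need many more subjects than an analysis of measured differences. These points are separate from who the reviewer is and whether that person is masked.

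**Working it through.** **Plan's own figure.** There is none to reproduce. The limit of 100 has no power calculation, and no efficiency or precision is stated for this endpoint.

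**Inputs.** From the documents: n = 50 (Section 4.0 minimum), n = 100 (Section 8.3 limit), and paired data (crossover). Assumed here: two-sided 5% level, standardized within-subject differences d of 0.3 to 0.5, and a sign test on one win/lose call per subject. The plan names no such test.

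**Efficiency.** The asymptotic efficiency of the sign test relative to the paired t-test is 4σ²f(0)², where σ² and f(0) are the variance and central density of the within-subject differences.

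| Distribution of differences (no ties) | Calculation | Efficiency |
|---|---|---|
| Uniform on (−1, 1) | 4 × 1/3 × (1/2)² | 0.33 |
| Normal | 4 × 1/(2π) = 2/π | 0.64 |
| Logistic | 4 × π²/3 × (1/4)² = π²/12 | 0.82 |
| t, 5 df | same formula | 0.96 |
| Laplace | 4 × 2 × (1/2)² | 2.0 (no loss) |

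Under normality 50 pairs of verdicts are worth about 50 × 0.637 = 32 measured pairs. Against the Wilcoxon signed-rank test the normal-case efficiency is 2/3.

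**Ties.** If a fraction q of subjects are truly equal and each is assigned a winner at random, the normal-case efficiency becomes (1 − q) × 2/π: 0.51 at q = 20% and 0.38 at q = 40%.

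**Power** (normal differences, no ties). The probability that a given arm wins is Φ(d). The measured analysis uses the noncentral t; the verdict uses the exact two-sided sign test, which rejects at 33 or more wins of 50, or 61 or more of 100, in either direction.

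| n | d | Φ(d) | Measured | Verdict | Actual level of sign test |
|---|---|---|---|---|---|
| 50 | 0.4 | 0.655 | 79% | 54% | 0.033 |
| 50 | 0.5 | 0.691 | 93% | 74% | 0.033 |
| 100 | 0.3 | 0.618 | 84% | 61% | 0.035 |

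Part of each gap is discreteness. With the sign test randomized to run at exactly 5%, its power is 60% (n = 50, d = 0.4) and 66% (n = 100, d = 0.3). That leaves gaps of 79 − 60 = 19 and 84 − 66 = 18 points.

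**Are the drawings collected?** The row for the current arm's paresthesia and pain map is treated differently in three schedules. The Synopsis schedule ticks enrollment, after implant, follow-up and exit. The Section 4.1 table ticks after implant, follow-up and exit. The table in Section 9.1.1 leaves the row blank. The visit descriptions in Sections 9.1.5 and 9.1.6 support follow-up and exit.

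**The case against.** The strongest reply is that the plan is silent here and has not chosen a poor method. Section 5.2 does not prescribe one forced call per subject and names no test. A reviewer who graded overlap in each arm before comparing them would also fit the words. The diagrams are kept, so nothing is lost from the data, and this is one of several secondary endpoints with no power claim attached. Measuring area is also not described anywhere, and percent overlap is bounded at 0 and 100, which makes exact normality doubtful.

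Much of this stands, and it rules out three stronger readings.

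- A reader might infer that the endpoint discards about a third of the information. That is the normal, no-tie case only; the documents give no SD, distribution or tie rate to fix it.
- A reader might infer from Section 1.0, where a cited study "showed that 10/19 patients had greater coverage", that ties will be common. The other 9 of 19 (47%) may be unchanged or lower, and the split is not given, so this is not a tie rate.
- A reader might infer that equal subjects must be given a winner. The text provides no tie outcome, but does not forbid one.

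What does not stand is the suggestion that silence makes the endpoint adequate. On any reading the stated output is which arm was superior, and scoring the diagrams later without a pre-specified method would be post hoc.

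**Conclusion.** The point holds in a limited form. The overlap endpoint is directional, has no tie outcome and cannot estimate the gain in coverage that motivates the trial. That conclusion needs no distributional assumption.

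The cost in efficiency is conditional on a win/lose analysis that the plan does not name. It runs from about two thirds lost (uniform differences) to nothing lost (Laplace), with 36% lost under normality and no ties, and more if tied subjects are assigned at random. The power figures share the normal, no-tie assumption and rest on assumed effect sizes.

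That percent overlap can be measured is a reasonable inference from the maps collected and from the percentage form of the primary endpoint; the documents do not state it. This is a worthwhile, low-cost improvement to a secondary endpoint and does not threaten the primary analysis.

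**What to change.** 1. Define the endpoint, for each arm, as the percent of the baseline pain-map area that is covered by paresthesia on the end-of-arm diagram.
2. Have the reviewer already foreseen in Section 5.2 score it, using the same written area method (for example a grid or pixel count) as the primary pain-map endpoint. That method is not yet described for either endpoint, so one text can serve both.
3. Compare the arms within subject in a crossover model with period and sequence terms. Report the mean difference with a 95% CI.
4. If a superior-arm verdict is kept, make it descriptive and add a no-difference category with a stated threshold.
5. Reconcile the schedules in the Synopsis, Section 4.1 and Section 9.1.1 on when the paresthesia and pain map is recorded.

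The cost is protocol and SAP wording plus modest scoring work on diagrams the visit descriptions already call for. No extra visit is needed. The draft case report forms are not in the text reviewed, so whether the diagram template suits area scoring should be checked before it is finalised.
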